9.4.3 Baseline Descriptive Statistics

Baseline population characteristics including gender, race, ethnicity, age, and BMI will be presented. Statistical analysis will not be performed on baseline characteristics.

9.4.4 Sub-Group Analyses

Subgroup differences between various age groups or races are not expected and the sample size may be too small to determine statistically significant differences, but exploratory analyses may be performed (particularly on gender differences).

9.4.5 Tabulation of Individual Participant Data

Not applicable.

9.4.6 Exploratory Analyses

Exploratory endpoints include characterization of systemic/mucosal humoral responses at all timepoints, as well as further characterization of the immune response through flow cytometric

phenotyping of lymphocytes, cytokine analysis, transcriptomics, and assessment of T-cell responses. Given the exploratory nature of these endpoints, what analyses will be possible depends heavily on the results. Standard methods of transcriptomic, T-cell activity, cytokine analysis, and immunophenotyping analysis will be performed, followed by more focused analyses based on those initial results.

Categorical endpoints will be analyzed using Fishers exact test. Logistic regression may be used to adjust for covariates. Continuous endpoints will be analyzed using t-tests. Regression models may be used to adjust for covariates. Generalized estimating equation (GEE) models may be used to examine longitudinal endpoints. All exploratory analyses will be performed at the .05 level with all publications noting the endpoints as exploratory and a discussion on the number of endpoints that have been analyzed will be included.

Rates of influenza disease among groups will be compared using analysis of variance testing and post-hoc Tukey.

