1 PROTOCOL SUMMARY

1.1 SYNOPSIS

Title:

Randomized, Double-Blinded, Placebo-Controlled, Phase 1 Study of the Safety and Immunogenicity of BPL-1357, a BPL-Inactivated, Whole-Virus, Universal Influenza Vaccine

Study Description:

This is a randomized, double-blinded, placebo-controlled, single-center, phase 1 clinical trial of β -propiolactone (BPL)-inactivated quadruple influenza virus cocktail vaccine (BPL-1357) administered intramuscularly (IM) or intranasally (IN) in 2 doses 28 days apart. Participants will be randomized to one of three groups for treatment assignment. The primary hypothesis is that IN and IM BPL-1357 will be well tolerated.

Objectives:

Primary Objective:

1. To assess the safety of BPL-1357 given IM or IN, compared to placebo.

Secondary Objective:

- 1. To further assess the safety of BPL-1357 given IM or IN, compared to placebo.
- 2. To assess the immunogenicity of BPL-1357 given IM or IN, compared to placebo.

Tertiary Objective:

- 1. To characterize the systemic and mucosal humoral immune responses induced by BPL-1357 given IM or IN, compared to placebo.
- 2. To further characterize the immune response induced by BPL-1357 given IM or IN through variable, diversity, and joining (VDJ) gene repertoire analysis, cytokine analysis, cytometry, transcriptomics, and assessment of T-cell responses.
- 3. To assess the rates of influenza disease among groups given IM or IN BPL-1357 compared to placebo.

Endpoints:

Primary Endpoints:

- 1. Type and severity (by grading) of adverse events (AEs) through vaccine 2 (V₂) day 28 (D28) [28 days after vaccine dose 2].
- 2. Type of serious adverse events (SAEs) through V₂D28 [28 days after vaccine dose 2].

Secondary Endpoints:

- 1. Safety
 - a. Type and severity (by grading) of AEs through V₂D182 [182 days after vaccine dose 2].

- b. Type of SAEs through V₂D182 [182 days after vaccine dose 2].
- 2. Immunogenicity
 - a. Antibodies against H1, H3, H5, and H7 head and stalk as measured by hemagglutination inhibition (HAI) or enzyme-linked immunosorbent assay (ELISA) from blood and mucosal samples at V₂D28.
 - b. Antibodies against N1, N3, N8, and N9 as measured by neuraminidase inhibition (NAI) or ELISA from blood and mucosal samples at V₂D28.

Tertiary Endpoints:

- 1. Additional antibody titer characterization via:
 - a. Antibodies against H1, H3, H5, and H7 head and stalk as measured by HAI or ELISA from blood and mucosal samples at V₁D7, V₁D14, V₁D28, V₂D7, V₂D14, V₂D56, and V₂D182.

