4 STUDY DESIGN

4.1 OVERALL DESIGN

This is a randomized, placebo-controlled, single-center, phase 1 clinical trial of BPL-1357 administered via IM or IN routes. The primary safety hypothesis is that BPL-1357 given IN or IM will be well-tolerated with minor side effects.

Participants will be randomized 1:1:1 to one of three groups:

- Group A will receive IM BPL-1357 plus IN placebo.
- Group B will receive IM placebo plus IN BPL-1357.
- Group C will receive IM and IN placebo.

This study will test a single dose of vaccine given at two timepoints 28 days apart. Group C will receive IM and IN placebo.

For each participant, the duration of study participation will be about 7 months (Figure 2). Participants will be followed regularly for 210 days to assess for side effects and to collect nasal mucosal and blood samples to evaluate immunity and characterize immune response. Participants will receive the intervention on 'vaccine 1 day 0' (V₁D0) and will return for followup on vaccine 1 day 7±1 14±2, and 28±2. They will receive the second dose of vaccine/placebo on 'day 28', referred to as 'vaccine 2 day 0' (V₂D0). Subsequent visits will be scheduled with respect to the timing of V₂D0 (i.e. V₂D7 will be scheduled for 7 days after V₂D0 and not 35 days after V₁D0, if there is disagreement between the two). Participants will return for follow-up on vaccine 2 day 7±2, 14±2, 28±7, 56±7, and 182±7 (Table 1). Participants will also complete a survey questionnaire at home for 7 days after each vaccine dose to further evaluate safety (APPENDIX A). Participants will be sent home with a thermometer to facilitate at home temperature monitoring and instructions will be provided (APPENDIX B). Participants who develop symptoms concerning for influenza-like illness (ILI) (including but not limited to rhinorrhea, sore throat, change in smell or taste, cough, wheezing, dyspnea, fatigue, weakness, malaise, dizziness, fever, chills, headache, myalgias, arthralgias, diarrhea) will contact the study team regarding evaluation. Those with confirmed influenza-like illness by the study team who are unable to be evaluated expeditiously at NIH will be instructed to perform an at-home nasal swab and/or nasal SAM and send the specimens in for testing. Collection and packing materials will be provided to participants either in person or will be mailed to participants. Detailed instructions for sample collection and packaging will be given to participants (APPENDIX C).

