- Antibodies against N1, N3, N8, and/or N9 as measured by NAI and/or ELISA from blood and mucosal samples.
- VDJ gene repertoire analysis.
- Cytokine analysis.
- Flow cytometric phenotyping of lymphocytes.
- Transcriptomic gene expression.
- T-cell responses.

Patients with ILI will perform at home nasal sampling with a nasal swab and/or SAM and ship specimens to NIH for testing or will be tested in clinic for influenza (and possibly, other respiratory pathogens).

Laboratory studies are generally performed in the NIAID LID with the exception of transcriptomic analysis which is sent to [name] at the Institute for Systems Biology.

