9.2 SAMPLE SIZE DETERMINATION

There will be 15 participants in each treatment group. The study will have adequate power to observe safety signals as defined by the 2 pausing criteria.

 A subject experiences an SAE that is unexpected (per the investigator's brochure or product label) and possibly, probably, or definitely related to a study agent or route of administration;

• A subject experiences two grade 3 or greater AEs that are unexpected (per the investigator's brochure or product label) and possibly, probably, or definitely related to a study agent or route of administration.

Table 7 gives the probability of meeting either criteria in just one arm under various true rates. The table shows that if the true rate in a single vaccine arm is 15% there would be a high probability of detecting the safety signal (power of 0.913). If we meet pausing criteria in both arms, then we also meet halting criteria for study.

Table 8. Probability of meeting pausing criteria

True rate of pausing	Probability of pausing
criteria 1 or 2 (%)	(≥ 1/15)
5%	0.537
10%	0.794
15%	0.913

We will also compare AE rates for the combined vaccine arms to the placebo arm at V_2D28 . We will use a 1-sided .05 level test for the comparison of proportions. With this test we will have 80% power if the true rate in the placebo arm is 5% and the true rate in the vaccine arms is 36%. We will also have 80% power if the true rate in the placebo arm is 10% and the true rate in the vaccine arms is 44%. (This calculation was performed using the SWOG statistical tool website with no continuity correction).

For the safety secondary objective we will compares AE rates in a similar manner but at the end of study, V_2D182 . For the immunogenicity secondary objective, we will compare antibodies against H1, H3, H5, H7, N1, N3, N8, and N9 from both blood and mucosal samples between all 3 arms at V_2D28 . With 15 participants in each arm there will be power of 0.82 to detect an effective size of 1.25 (the effective size is the mean/std) using a two-sided 0.05/3=.0167 level t-test. The level of the test has been adjusted to control for the 3 comparisons between all groups. A similar analysis will be performed at other timepoints for one of the exploratory objectives.

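### Influenza disease, a yes/no outcome with 15 participants per arm, is assigned to ANOVA and Tukey as an unexplained exception to the section's exact-test rule, and in sparse tables that choice can change the result

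*Combined protocol and SAP*

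**What the plan says.** The synopsis (section 1.1) lists a tertiary objective: "To assess the rates of influenza disease among groups given IM or IN BPL-1357 compared to placebo". The matching endpoint is named only as influenza disease, without a case definition, denominator or expected rate. Cases come to light through illness: "Patients with ILI will perform at home nasal sampling with a nasal swab and/or SAM and ship specimens to NIH for testing", or they are tested in clinic (section 8.2.3).

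Section 9.4.6 gives a general rule for exploratory endpoints: "Categorical endpoints will be analyzed using Fishers exact test". It also sets a significance level: "All exploratory analyses will be performed at the .05 level". Its last sentence then treats this one endpoint differently: "Rates of influenza disease among groups will be compared using analysis of variance testing and post-hoc Tukey". No reason is given.

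On size, section 9.2 says: "There will be 15 participants in each treatment group". On follow-up, section 4.1 says: "Participants will be followed regularly for 210 days".

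**The concern.** ANOVA and Tukey compare means under a normal model with a common residual variance. A per-participant infection outcome is 0 or 1, and with 15 per arm one or both vaccine arms may have no cases and hence no sample variance. The p-values then rest on an approximation at its weakest, although an exact test is available and is already the section's default.

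This is the only clinical disease outcome compared with placebo. If the planned test and the section's general rule fall on opposite sides of .05, the reading of a vaccine-placebo difference depends on which sentence is followed. That should be settled before unblinding.

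**Working it through.** The plan gives no power, attack rate or expected case count for this endpoint, so there is no figure to reproduce.

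**Inputs.** n=15 per arm, N=45 (section 9.2). Allocation: "Participants will be randomized 1:1:1 to one of three groups" (section 4.1). Level .05 (section 9.4.6); sidedness is not stated, and all tests below are non-directional. Assumptions: one yes/no outcome per participant, and the case counts shown.

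**Formulas**, for case counts x in each arm:
- Within-group sum of squares: SSW = Σ x(1 − x/15); MSW = SSW/42.
- Between-group sum of squares: SSB = 15 Σ (arm proportion − overall proportion)²; F = (SSB/2)/MSW on 2 and 42 df.
- Tukey: q = |difference in proportions| / √(MSW/15), referred to the studentized range for 3 groups and 42 df.
- Fisher-Freeman-Halton (three groups), when all m cases fall in one arm: p = 3·C(15,m)/C(45,m) for m = 3, 4 or 5.
- Pairwise Fisher, 0 against m cases: p = 2·C(15,m)/C(30,m).

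**Cases 0/0/3 (IM/IN/placebo).**
- SSB = 15[2(0.0667²) + 0.1333²] = 0.40; SSW = 3(1 − 3/15) = 2.40.
- F = 0.20/(2.40/42) = 3.50, p=0.039.
- q = 0.20/√(0.05714/15) = 3.24, p=0.068; the Tukey 95% interval for the difference is −0.012 to 0.412.
- Exact three-group p = 3·455/14190 = 0.096.
- Pairwise Fisher p = 2·455/4060 = 0.224.

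**Cases 0/0/4.**
- SSB = 0.711; SSW = 4(1 − 4/15) = 2.933.
- F = 0.3556/0.06984 = 5.09, p=0.0105.
- q = 0.2667/√(0.06984/15) = 3.91, p=0.0225 for each vaccine arm against placebo.
- Exact three-group p = 3·1365/148995 = 0.0275.
- Pairwise Fisher p = 2·1365/27405 = 0.0996.

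**Comparison of tables**

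| Cases IM/IN/placebo | ANOVA p | Exact three-group p | Tukey p, vaccine vs placebo | Pairwise Fisher p, unadjusted |
|---|---|---|---|---|
| 0/0/3 | 0.039 | 0.096 | 0.068 | 0.224 |
| 0/0/4 | 0.0105 | 0.0275 | 0.0225 | 0.0996 |
| 0/0/5 | 0.0024 | 0.0074 | 0.0065 | 0.042 |
| 1/1/4 | 0.186 | 0.330 | 0.249 | 0.330 |

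The tests disagree at .05 in the three-group comparison at 0/0/3 and in the pairwise comparison at 0/0/4.

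**Type I error.** Given exactly three cases and no vaccine effect, the F test rejects whenever all three fall in one arm, which happens 9.6% of the time; Tukey and the exact test never reject. Averaged over all outcomes, with a common attack rate assumed between 2% and 20%, the size is 0.5% to 4.3% for the F test, 0.03% to 4.5% for Tukey and 0.03% to 3.2% for the exact test. None exceeds 5%.

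**The case against.** The strongest reply has four parts.

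1. The influenza sentence is specific and the Fisher sentence is general, so an analyst would know to run ANOVA. This stands: it is an unexplained exception rather than a contradiction that leaves the method undecided.
2. Overall error is controlled, and part of the gap is the conservatism of Fisher's test. This also stands. At 0/0/4 the exact three-group test itself rejects.
3. The F test is close to what an uncorrected test of proportions would give. At 0/0/3 the Pearson chi-square is 45·0.40/2.80 = 6.43, p=0.040, and section 9.4.1 uses uncorrected tests of proportions for adverse events. This shows that the issue is approximation against exactness in sparse data, which the section's own exact-test rule already addresses.
4. The endpoint is tertiary, section 8.2.1 says clinical evaluations are not for efficacy, and publications must call it exploratory. This limits the consequence.

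A reader might also infer three stronger claims, which the documents do not support:
- That three cases could be declared a protective effect. At the planned 15 per arm only the non-directional F test crosses .05, and Tukey, the step that would name an arm, gives 0.068. Three placebo cases suffice for Tukey only if the placebo arm ends up smaller (for example 15/15/12, p=0.028), which is not the planned design.
- That the planned p-values are too small by a fixed factor. The gap depends on the table: at 1/1/4 it is 0.330/0.186 = 1.8 for the three-group tests and 0.330/0.249 = 1.3 for the pairwise tests.
- That the .05 level implies unadjusted gene-by-gene testing. The section refers to standard transcriptomic methods and does not say this.

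**Conclusion.** The concern holds in a limited form. The planned method suits means rather than a sparse yes/no outcome, it departs without explanation from the rule stated just before it, and it can change the result: the three-group result at three cases (0.039 against 0.096) and the pairwise result at four (0.0225 against 0.0996 unadjusted), when all cases are in placebo.

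It is not a problem of overall false-positive rate. The conclusion rests on reading influenza disease as one yes/no outcome per participant, on 15 analysed per arm, and on few cases occurring. The last is plausible with 45 participants over 210 days but is not stated in the plan. Because the endpoint is tertiary and labelled exploratory, this is a correction worth making rather than a threat to the trial's main conclusions.

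**What to change.** Replace the last sentence of section 9.4.6 with:

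> The proportion of participants with influenza disease will be reported by group with exact confidence intervals and compared across the three groups with the Fisher-Freeman-Halton exact test; pairwise Fisher's exact tests will be adjusted for the three comparisons (e.g. Holm).

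Add a case definition and denominator, since the plan gives neither. The pairwise adjustment should stay: Tukey covers three comparisons, and unadjusted Fisher tests would lose that protection.

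The cost is a few sentences of text and no change to conduct or sample size. Exact p-values are conservative and will usually be larger. Under Holm, the vaccine-placebo comparison at 0/0/5 becomes 3 × 0.042 = 0.126, and at 0/0/6 it is 3 × 2·5005/593775 = 0.0506, so neither is significant. If that is judged too severe, a closed procedure also controls the familywise error with three groups: test pairs at .05 only after the three-group exact test rejects. At 0/0/5 it would declare a difference (0.0074, then 0.042). Either rule is acceptable if it is written down before unblinding.

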10 REGULATORY AND OPERATIONAL CONSIDERATIONS

10.1 Informed Consent Process

10.1.1 Consent/Assent Procedures and Documentation

Informed consent is a process where information is presented to enable persons to voluntarily decide whether or not to participate as a research participant. It is an ongoing conversation between the human research participant and the researchers, which begins before consent is given and continues until the end of the participant's involvement in the research. Discussions about the research will provide essential information about the study and include purpose, duration, experimental procedures, alternatives, risks, and benefits. Participants will be given the opportunity to ask questions and have them answered.

The participants will sign the informed consent document prior to undergoing any research procedures. The participants may withdraw consent at any time throughout the course of the trial. A copy of the informed consent document will be given to the participants for their records. The researcher will document the signing of the consent form in the participant's medical record. The rights and welfare of the participant will be protected by emphasizing to them that the quality of their medical care will not be adversely affected if they decline to participate in this study.

The study will be introduced and explained to the potential participant during the screening visit on protocol 11-I-0183, which will be within 60 days of the V_1D0 visit. Informed consent will be obtained at the V_1D0 clinic visit prior to enrolling into the study. Consent will be obtained in person by the PI and/or equally qualified designee.

10.1.2 Consent for Minors When They Reach the Age of Majority

Not applicable.

10.1.3 Telephone Consent

Not applicable.

10.1.4 Telephone Assent

Not applicable.

10.1.5 Participation of Subjects Who Are/Become Decisionally Impaired

Adults unable to give consent are excluded from enrolling in the protocol. However, re-consent may be necessary and there is a possibility, though unlikely, that subjects could become decisionally impaired. Because there is no prospect of direct benefit from participation in this study, if a subject becomes decisionally impaired while on study, they may continue to undergo safety evaluations if deemed appropriate by the PI in consultation with the SMM. All remaining research interventions will be discontinued.

10.1.1 Participation of NIH Employees

For NIH employee participants, consent will be obtained by an individual independent of the employee's team whenever possible. Otherwise, the consent procedure will be independently monitored by the CC Department of Bioethics Consultation Service in order to minimize the risk of undue pressure on the staff member. Those in a supervisory position to any employee and coworkers of the employee will not obtain consent.

10.2 STUDY DISCONTINUATION AND CLOSURE

The study may be temporarily suspended or permanently terminated as described in the halting rules (section 8.4.6). In addition to the reporting described in that section, the PI will promptly contact the study participants, provide the reason(s) for the termination or suspension, and, if applicable, inform them of changes to study visit schedule.

The PI will consult with the IRB, in addition to the CSO, DSMB, and FDA prior to resuming the study following a halt.

10.3 CONFIDENTIALITY AND PRIVACY

All records will be kept confidential to the extent provided by federal, state, and local law. The study monitors and other authorized representatives of the sponsor may inspect all documents and records required to be maintained by the investigator, including but not limited to, medical records. Records will be kept locked and data will be coded. Any personally identifiable information maintained for this study will be kept on restricted-access computers and networks. Personally identifiable information will only be shared with individuals authorized to receive it under this protocol. Individuals not authorized to receive personally identifiable information will be provided with coded information only, as needed. Clinical information will not be released without written permission of the participant, except as necessary for monitoring by IRB, the FDA, the NIAID, the Office for Human Research Protections (OHRP), or the sponsor's designee.

Access to research samples will be limited using a locked freezer in a locked laboratory. Samples and data will be stored using codes assigned by the investigators. Data will be kept in password-protected computers. Only investigators and their designees will have access to the samples and data. Samples will initially be stored in laboratories of the PI and associate investigators. Samples will be tracked using a database located on password-protected computers, which will be maintained by the investigators and their designees. Only investigators and their designees will have access to this database.

Any loss or unanticipated destruction of samples (for example, due to freezer malfunction) or data (for example, misplacing a printout of data with identifiers) that meets the definition of a reportable event will be reported to the IRB according to Policy 801.

Participants may decide at any point during study participation or after not to have their samples stored. In this case, the PI will destroy all known remaining samples and report what was done to both the participant and to the IRB. This decision will not affect the subject's participation in this protocol or any other protocols at NIH.

To further protect the privacy of study participants, a Certificate of Confidentiality has been issued by the NIH. This certificate protects identifiable research information from forced disclosure. It allows the investigator and others who have access to research records to refuse to disclose identifying information on research participation in any civil, criminal, administrative, legislative, or other proceeding, whether at the federal, state, or local level. By protecting researchers and institutions from being compelled to disclose information that would identify research participants, Certificates of Confidentiality help achieve the research objectives and promote participation in studies by helping assure confidentiality and privacy to participants.

